Center for Epidemiological Studies Depression Scale – Revised (CESD-R) (Appendix): The CESD-R (Eaton et al., 2004) is a revised version of the Center for Epidemiological Studies Depression Scale (CES-D; Radloff, 1977). It is a 20-item self-report symptom severity measure of depression. Patients endorse one of the answer choices (Not at all or less than 1 day, 1-2 days, 3-4 days, 5-7 days, nearly every day for 2 weeks) for each of the statements that list certain behaviors or feelings common to depression (in the past week). For example, items address appetite, sleep, weight, suicide, self-harm, attention, happiness, and interest. Participants will complete this form at baseline, midpoint, endpoint, and follow-up timepoints.

Clinical Global Impression – Improvement Scale (CGI-I) and severity scale (CGI-S) (Appendix): The single-item CGI-I, which ranges from 1 (very much improved) to 7 (very much worse), is commonly used in clinical trials (Guy, 1976). Participants will complete a CGI-I for MDD symptoms (CGI-P MDD) and the clinician will complete a CGI-I for MDD symptoms (CGI-MDD) and overall symptoms (CGI-global). The CGI-I ratings will be secondary outcome measures and will also be used to determine clinical deterioration of MDD via weekly administration through REDCap (link to be sent via email or in-app message) (see Minimizing Risks, below). The CGI also has a severity scale (CGI-S) which is rated by the clinician at baseline as well as the following assessments. The CGI-S determines the patient's overall level of symptom severity, in comparison to other patients the clinician has treated or assessed with the same diagnosis.

Patient Health Questionnaire-9 (PHQ-9) (Appendix): The PHQ-9 (Spitzer, Kroenke, & Williams, 1999) is a self-report measure of depression severity includes 9 Likert scale items ranging from 0 (*not at all*) to 3 (*every day*). The PHQ-9 will be used as an initial screening measure to determine symptom severity for inclusionary purposes, as well as at the midpoint, post-treatment, and 3-month follow-up assessments.

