Patient Health Questionnaire-8 (PHQ-8) (Appendix): The PHQ-8 is a revised version of the PHQ-9 less item #9 (thoughts of death and self-harm). Research shows that the PHQ-8 is highly correlated with the PHQ-9 (>99%) and shows highly similar sensitivity and specificity (Wu et al., 2020). It will be re-administered weekly prior to a patient's appointment with their study clinician. REDCap link to be sent via email or in-app message.

Columbia-Suicide Severity Rating Scale (C-SSRS) (Appendix): The C-SSRS (Posner et al., 2008) is a gold-standard, clinician-administered assessment of suicidal ideation and suicide behaviors. The baseline version, which assesses both lifetime and recent time frames, will be used to establish eligibility at the baseline/screening visit. The "Update" version, which assesses suicide risk since the last assessment, will be used at subsequent study administrations.

Depression, Anxiety, and Stress Scale (DASS-21): (Appendix). The DASS-21 is a 21iitem self-report questionnaire created from a set of three self-report scales with 7 items each. The subscale groups include depression, anxiety, and stress scale (Lovibond & Lovibond, 1995).

Assessment of Functioning and Quality of Life

Work and Social Adjustment Scale (WSAS) (Appendix): The WSAS is a 5-item, selfreport measure of impairment in occupational, social, and family domains (Mundt et al., 2002). Items are measured on 9-point Likert scales ranging from 0 (no impairment at all) to 8 (very severe impairment).

Quality of Life Enjoyment and Satisfaction Questionnaire – Short Form (Q-LES-Q-SF) (Appendix). The Q-LES-Q-SF (Endicott, Nee, Harrison, & Blumenthal, 1993) is a 16-item selfreport measure of subjective quality of life. Higher scores correspond with greater ratings of quality of life. The Q-LES-Q-SF has strong psychometric properties (Endicott et al., 1993).

Assessment of Expectancy, Motivation and Satisfaction

Credibility/expectancy questionnaire (CEQ) (Appendix): This 6-item, self-report, Likerttype questionnaire assesses patients' judgments about the credibility of the treatment rationale and treatment expectancy (Borkovec & Nau, 1972). It has good reliability (α =.81-.86), and validity is evident in its ability to differentiate between treatment rationales (Devilly & Borkovec, 2000).

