Treatment Utilization Questionnaire (TUQ) (Appendix): This 3-item self-report form measures how much time participants are practicing treatment skills both on and off the app.

*Technologist Interview Notes* (Appendix): This interview guide asks about credibility/expectancy, client satisfaction, and improvements at post-treatment.

Life Events Questionnaire (Appendix): This question will be used to assess whether any major life events occurred since the previous assessment that might have had a psychological impact on the subject.

Therapist Satisfaction Questionnaire: (Appendix). This self-report form for clinicians will assess their satisfaction with using this app treatment approach.

Everyday Discrimination Scale Short Version: (Appendix). This 5-item self-report form asks about participants' experiences with discrimination in their daily life (Sternthal, Slopen, & Williams, 2011).

Adverse Event Form and Log (AE Form) (Appendix). This form probs for any major events or concerns (i.e., adverse events) since the last time the form was filled out.

Self Help Questionnaire: (Appendix) This self-report form collects information about any additional self-help behaviors that could have impacted their well-being or depression since beginning treatment.

IE Training and Qualifications, and Procedures to Ensure Assessment Integrity and Interrater Reliability: Assessments will be conducted by an IE who has a Master's or Doctoral degree in clinical psychology or related mental health field. The IE will be otherwise uninvolved in study procedures. Training and reliability checks will be done to ensure that IEs conduct ratings in a uniform way. IEs will first receive instruction in the MINI and HAM-D from a gold-

standard expert rater, prior to beginning as an IE. The IE will be supervised at minimum twice monthly. The IE will be required to demonstrate reliability on the HAM-D at a criterion of .80 ICC, compared to measures rated by a gold-standard rater. All assessments will be audiotaped for reliability ratings. To reduce rater drift, a trained reliability rater meeting the same qualifications as the IE will review 15% of randomly selected audiotaped interviews. If reliability falls below .75, we will institute retraining procedures.

Measure	Baseline	Baseline Re-assess	Weekly	Mid- Treatment Assess (wk 4)	Post- Treatment Assess (wk 8)	3-month Follow-up
Treatment	✓					
History Checklist						
Treatment						
History						

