Medication	•					
Treatment	√					
History						
Psychosocial Life Events						
Question		✓		✓	✓	~
AE Form		J		J	J	、
CONCOM Form		J		J	J	v
MINI	✓	•			•	
HAM-D	V	✓		J	J	v
C-SSRS Lifetime	v					-
C-SSRS Update		v		J	\	√
CGI–S	✓	V		V	V	v
CGI–MDD, CGI-		√		√	√	\
Global		_				
Technologist						✓
Interview Notes						
Demographics	√					
Lifetime	√					
Psychiatric						
Medication Form						 
PHQ-9	✓	✓		✓	✓	√
CGI-P (MDD)		✓	✓	✓	√	✓
PHQ-8			√			
CEQ	✓			✓		
URICA	✓					

Table 1 Assessment Measures by Occasions for the Open Trial.

CESD-R	✓	 ✓ 	√
Q-LES-Q-SF		v	v
WSAS 🗸		v	1
DASS-21	_	v	1
Everyday Discrimination Scale		~	-
Self Help Questionnaire		~	~
CSQ	J	\	
Treatment Utilization Questionnaire		~	~
App Feedback Questionnaire (Baseline)			
App Feedback Questionnaire (Midpoint)	✓ ✓		
App Feedback Questionnaire (Endpoint)		~	
uMARS		✓	
Therapist Satisfaction Questionnaire		~	

If more than ten days elapse between a patient's initial baseline screening assessment and the start of treatment, the study IE would re-administer select forms, including an additional HAM-D form.

Despite our best efforts to retain participants, we do expect dropouts. Except for subjects who withdraw consent to participate, all who are withdrawn or drop out of the study will be asked to complete all scheduled assessments and we will provide remuneration for participation in assessments.

In addition to the assessment measures in Table 2, de-identified data from sensors in participants' mobile phones will also be collected via the CBT and Habits apps, to inform design and improvement of the app.

B. Drugs to be used

Not applicable

C. Devices to be used

Participants will download the CBT for MDD and Habits apps onto their personal smartphone devices.

D. Procedures, surgical interventions, etc.

Not applicable

E. Data to be collected and when the data will be collected

See above for the assessment schedules and assessment batteries for each phase.

VI. BIOSTATISTICAL ANALYSES

The IE and the RAs will play the primary role in data entry. Data will be entered in REDCap, a HIPAA-compliant, Partners-approved platform for electronic data capture that streamlines data collection and management, and ensures data integrity, resulting in improved data quality and reduced costs. For more information on REDCap, please see section IX, "Monitoring and Quality Assurance."

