[name] will be responsible for data management and analysis. All project staff will receive training in data management and data confidentiality procedures. Data checks will be done regularly to assure that all forms are entered and available for analysis. Questions or problems will be resolved promptly by communication between study staff. Data and analysis files will be backed up on the lab server and may also be stored in separate locked cabinets.

To characterize our sample, data will be displayed graphically, and summary statistics (e.g., means and frequencies) will be calculated for all variables, including demographic and clinical descriptors (e.g., from the MINI).

Prior to data analysis, all major variables will be screened for inconsistent or abnormal values. Continuous measures will be assessed for skewness and outliers (based on model residuals), and, if needed, will be transformed to better meet modeling assumptions of normality and homogeneity of variance. A two-tailed p-value <.05 will be considered evidence of statistical significance for the primary and secondary outcomes.

A. Specific data variables being collected for the study (e.g., data collection sheets)

Specific variables being collected, and their timeline are presented in Table 1, and described in the Study Procedures section.

B. Study endpoints

Primary endpoints: Feasibility and acceptability of the combined digital CBT plus virtual treatment.

Hypothesis 1a: We hypothesize that digital CBT plus virtual treatment will be feasible (based on uptake, engagement and drop-out rates).

Hypothesis 1b: We hypothesize that digital CBT plus virtual treatment will be deemed acceptable both to patients and clinicians (based on descriptive statistics of patient

expectancy and satisfaction, app use, app feedback, clinician ratings, as well as qualitative feedback).

Secondary endpoints: Preliminary efficacy of digital CBT plus virtual treatment for primary outcomes (i.e., reduction in severity of depressive symptoms) and secondary outcomes (e.g., quality of life at post-treatment, social and occupational functioning at post-treatment).

Hypothesis 2a: We hypothesize that participants receiving digital CBT plus virtual treatment will evidence statistically significant reductions in HAM-D scores from baseline to post-treatment (week 8).

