Hypothesis 2b: We hypothesize that participants receiving digital CBT plus virtual treatment will evidence statistically significant improvement on secondary clinical outcome measures (i.e., functional impairment (WSAS) and quality of life (Q-LES-Q)) from baseline to post-treatment (week 8).

C. Statistical methods

Primary endpoints: feasibility and acceptability of the combined digital CBT plus virtual treatment.

Analysis:

We will examine feasibility (H1a) and acceptability (H1b) by reporting:

- 1. Refusal and dropout rates and reasons
- 2. Patient satisfaction, as measured by the Client Satisfaction Questionnaire
- 3. Patient feedback, as measured by Mobile Application Rating Scale user version
- 4. Patients' credibility and expectancy ratings for the open-label treatment, as measured by the Credibility/Expectancy Questionnaire
- 5. Treatment utilization, as measured by the Treatment Utilization Questionnaire

Secondary endpoints: preliminary efficacy of digital CBT plus virtual treatment for reducing severity of depression symptoms, and improving quality of life and functional impairment

Analysis:

Intention-to-treat mixed model analyses with repeated measures (baseline, mid-treatment, post-treatment) will be used to examine differences between pre- and post-treatment depression (HAM-D scores), using a two-tailed α -level of .05. The pre- to post-treatment effect size will be calculated. Similar analyses will also be conducted for change in functional impairment (WSAS) and quality of life (Q-LES-Q) over the course of treatment. We will not adjust for multiple testing among secondary outcomes based on the recommendation of Cook and Farewell (1996), who argue that multiplicity adjustments are not necessary if separate test results are interpreted marginally and address different aspects of the patient experience and decision-making process rather than alternative assessments of efficacy.

D. Power analysis

With n=28, we will have > 80% power to detect pre- to post-treatment effect sizes of d \ge 1.37 (very large effect sizes). The estimate of the detectable effect size is based on a single degree of freedom contrast in a paired means test, implemented in SAS for Windows version 9.4. The

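### Does the plan need to say which of two pre-treatment HAM-D ratings is the analysis baseline?

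*Combined protocol and SAP*

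**What the plan says.** The text after Table 1 (Study Procedures) sets the trigger: more than ten days between a patient's "initial baseline screening assessment and the start of treatment". In that case "the study IE would re-administer select forms, including an additional HAM-D form". Table 1 has a separate column, "Baseline Re-assess", next to the Baseline column, and the HAM-D row is ticked in both.

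Section VI.C plans intention-to-treat "mixed model analyses with repeated measures (baseline, mid-treatment, post-treatment") for the HAM-D, and a pre- to post-treatment effect size. Hypothesis 2a in Section VI.B is worded as a reduction from baseline to week 8. Neither section says whether baseline is the first rating, the last one or an average. Section VI.B lists feasibility and acceptability as the primary endpoints and HAM-D efficacy as secondary.

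Two further entries bear on the reading. The CGI-I forms are ticked at the re-assessment but not at Baseline, and Measures Descriptions says of them that "The CGI-I ratings will be secondary outcome measures". The C-SSRS at the re-assessment is the Update version, "which assesses suicide risk since the last assessment, will be used at subsequent study administrations".

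**The concern.** A delayed participant brings two scores to a model with one slot for them. There is no control arm to cancel a change between the two ratings, so the choice moves the estimate directly. With the first rating, any improvement or worsening while waiting is counted in the pre-post change; with the later one it is not.

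The wording can be read either way. One column is simply called Baseline and the repeat is described as additional, which favours the first score. The first visit is also called the initial baseline, the repeat is triggered by delay, and VI.C contrasts pre-treatment with post-treatment, all of which favour the later score. At stake are the size of the reported effect and, in principle, the freedom to choose a rating after seeing results. If the CGI-I were judged against the first visit and the HAM-D against the second, two outcomes in one person would also start from different points.

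**Working it through.** **1. The plan's own figure.** Section VI.D uses n = 28, two-sided alpha 0.05, power 0.80, pre-post correlation 0.18 and a doubling of the SD. In baseline SD units, the SD of change is √(1 + 2² − 2 × 0.18 × 2) = √4.28 = 2.069. The exact paired t-test detects 0.5492 × 2.069 = 1.14 at n = 28, not the stated 1.37. The stated figure matches n = 20 (0.6604 × 2.069 = 1.37). Power at 1.37 with n = 28 is 92.2%, so the claim of more than 80% power remains true. This mismatch is separate from the baseline question. The yardsticks below are the meta-analytic effect cited in VI.D, 1.79, and its lower confidence limit, which is also 1.37.

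**2. Size of the shift.** With f the share re-assessed and δ the mean fall between the two ratings in baseline SDs, and the standardising SD held fixed:

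shift = f × δ

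The documents give neither quantity. The assumed range is f from 0.10 to 0.50 (about 3 to 14 of 28) and δ from −0.3 to +0.5. A row with f = 1 is added as an extreme. Each power is for the effect left when the later rating replaces the first.

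| f | δ | shift | % of 1.79 | power, first-rating effect 1.79 | power, first-rating effect 1.37 |
|---|---|---|---|---|---|
| 0.50 | −0.3 | −0.15 | −8.4% | 99.8% | above 92.2% |
| 0.25 | 0.3 | 0.075 | 4.2% | 98.8% | 89.1% |
| 0.50 | 0.5 | 0.25 | 14.0% | 96.7% | 78.9% |
| 1.00 | 0.5 | 0.50 | 27.9% | 88.9% | 57.4% |

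With no shift, power is 99.3% at 1.79 and 92.2% at 1.37.

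**3. Against sampling error.** The standard error of the mean change is 2.069/√28 = 0.391, and the 95% half-width is 2.052 × 0.391 = 0.80. The middle case (0.075) is about 9% of that half-width. The largest shift in the assumed range (0.25) is about 31%.

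**4. Rejection with no treatment effect.** If the first rating is used and the only change is the one before treatment, shifts of 0.075, 0.15 and 0.25 give two-sided rejection of 5.4%, 6.6% and 9.5%. These are not error rates for Hypothesis 2a, which concerns change from baseline and not an effect of treatment. The single-arm design already counts eight weeks of natural change, whichever rating is used.

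**5. Choosing after the fact.** This was simulated with no drift, 25% to 50% re-assessed, an assumed correlation of 0.5 to 0.85 between the two ratings, and 40,000 trials per setting. Always taking the rating that shows more improvement leaves two-sided rejection at about 5.0%; rejection in the direction of improvement rises from the nominal 2.5% to about 2.9% to 3.3%. Only counting a trial as positive when either rating gives p < 0.05 in either direction raises the total, to about 5.7% to 6.7%.

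**6. Do the other forms settle the reading?** The C-SSRS Update covers the time since the previous assessment and is used in the same way at weeks 4 and 8 and at follow-up. It refers back one visit whatever the analysis baseline is. For the CGI-I, Section VI.C plans no analysis, Hypothesis 1b in the Specific Aims lists CGI ratings under acceptability, and the CGI also serves to detect deterioration. The form itself is in an appendix that was not available, so its reference period cannot be checked.

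**The case for a change.** The best case for a change is that two competent analysts could choose differently, that a pre-post effect size is what readers will compare with the 1.79 from earlier trials, and that one sentence in VI.C would remove the doubt without new data.

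Much of this stands. The definition is missing, and the share re-assessed and the drift are unknown. If most participants waited, improved noticeably meanwhile, and the true effect were near 1.37, the choice could matter to significance as well as to the estimate.

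That needs several unfavourable assumptions together, and nothing in the documents points to them. The argument from the CGI-I and C-SSRS rows does not add weight: one has no planned analysis in VI.C and the other says nothing about the HAM-D baseline. Nor is one rule clearly better. Taking the last rating before treatment is a common-sense choice, but outcomes that were not repeated would keep their first-visit value, so the HAM-D could start from a later date than the WSAS or Q-LES-Q. The lower part of Table 1 has lost its column alignment in the text reviewed, so which self-report forms are repeated cannot be told.

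**Conclusion.** No change follows. This is a missing detail that an analyst can fill sensibly: both ratings precede treatment, come from the independent evaluator on the same scale, and give a valid pre-post contrast for a secondary endpoint. Under the assumed 10% to 50% re-assessed and −0.3 to +0.5 SD of change, the estimate moves by −0.15 to +0.25 SD, or −8% to +14% of 1.79, well inside the 0.80 half-width. If the effect is near 1.79, the significance of Hypothesis 2a is unlikely to depend on the choice. The conclusion rests on those assumed figures and on a fixed standardising SD; re-assessment of nearly everyone with a large drift would weaken it.

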power model used a two-sided alpha=0.05, a power of 0.80, assumed a pre- to-post-treatment correlation of 0.18, and a doubling of the standard deviation from pre- to post-treatment. The pre- to post-treatment correlation estimate was based on the mean pooled correlation between pre-test and post-test HAM-D scores in 14 CBT trials for adult depression (Cuijpers et al., 2016); with higher pre-post correlations, smaller effect sizes would be detectable in other secondary outcomes. The anticipated increase in outcome standard deviation was based on observations reported in treatment studies with participants with MDD, which reported pre- to post-treatment standard deviation increases in observed HAM-D scores in the range of 161-191% (Jarrett et al., 1999; Elkin et al., 1989; Goldberger et al., 2011). We further assumed no drop-out by the end of treatment, similar to what we observed in pilot studies for similar app-treatment for body dysmorphic disorder ([name] et al., 2020); if drop-out was 20%, we would only be able to detect effect sizes of $d \ge 1.55$. For comparison, in a meta-analysis of randomized controlled treatment trials that included internet CBT (iCBT) for persons with MDD (Andrews et al., 2018), the observed median percentage of participants randomized who finished the treatment course was 66% (50/64 trials) and the interquartile range was 29% (Q1 52%, Q3 80%). Large pre-to post-treatment effect sizes for CBT treatments among patients with MDD are to be expected, based on a meta-analysis by Cuijpers and colleagues (2016), which found that the mean pre-post standardized mean difference (i.e., effect size) in 14 CBT trials was 1.79, 95% CI: [1.37, 2.21].

VII. RISKS AND DISCOMFORTS

A. Complications of surgical and non-surgical procedures

Not applicable

B. Drug side effects and toxicities

Not applicable

C. Device complications/malfunctions

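### Must the plan name the SD behind the HAM-D pre-post effect size, and the covariance structure of the mixed model?

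*Combined protocol and SAP*

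**What the plan says.** Section VI.C plans "Intention-to-treat mixed model analyses with repeated measures (baseline, mid-treatment, post-treatment") to compare HAM-D before and after treatment at a two-tailed level of 0.05. It then adds: "The pre- to post-treatment effect size will be calculated". No formula, SD or confidence interval is given for that effect size. No covariance structure is named for the model.

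The opening of Section VI says that continuous measures, if needed, "will be transformed to better meet modeling assumptions of normality and homogeneity of variance". It also plans summary statistics, with means as an example, for all variables.

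Section VI.D speaks of effect size in three places, each time without naming its SD:

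- At n=28, "we will have > 80% power to detect pre- to post-treatment effect sizes of d" ≥ 1.37.
- On attrition, "if drop-out was 20%, we would only be able to detect effect sizes of" d ≥ 1.55.
- From the cited meta-analysis, "the mean pre-post standardized mean difference (i.e., effect size) in 14 CBT trials was 1.79, 95% CI: [1.37, 2.21"].

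The power model "assumed a pre- to-post-treatment correlation of 0.18, and a doubling of the standard deviation from pre- to post-treatment". The doubling is attributed to studies reporting "standard deviation increases in observed HAM-D scores in the range of 161-191"%.

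Section VI.B makes feasibility and acceptability the primary endpoints and places HAM-D change under the secondary endpoints.

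**The concern.** If the SD stayed about the same from baseline to week 8, the baseline, pooled and post-treatment SDs would give similar answers and leaving the choice open would matter little. This plan expects the opposite. With the SD doubling and a weak correlation, the SDs in common use differ by a factor of up to 2.07.

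The trial has one arm. At a change of 1.79 baseline SDs the paired test has 99% power at n=28, so a significant result would say little and readers would look to the effect size. An SD chosen after the data are seen could make the same result look in line with the cited CBT trials or well below them.

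The second worry is smaller. A three-visit model fitted with equal variances would be wrong if the variance quadruples, and Section VI lists homogeneity of variance among the modeling assumptions.

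**Working it through.** **Inputs (Section VI.D):** n=28, paired test, two-sided alpha 0.05, power 0.80, pre-post correlation r=0.18, post-to-pre SD ratio k=2. The baseline SD is set to 1.

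**Candidate SDs**

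- Change SD: √(1 + k² − 2rk) = √(1 + 4 − 0.72) = √4.28 = 2.069
- Pooled SD (root mean square): √((1 + 4)/2) = 1.581
- Post-treatment SD: 2

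**The plan's own detectable effects.** The noncentral t gives the detectable change in change-SD units; multiplying by 2.069 gives baseline-SD units.

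| n | change-SD units | baseline-SD units |
|---|---|---|
| 28 | 0.549 | 1.14 |
| 22 (28 less about 20%) | 0.626 | 1.30 |
| 20 | 0.660 | 1.366 |
| 16 (20 less 20%) | 0.7495 | 1.551 |

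The stated 1.37 and 1.55 do not come out at n=28 and 22 on the baseline, pooled or post-treatment SD. At n=28 the pooled and post-treatment values are 0.72 and 0.57. Searching n from 6 to 60 over the baseline, average, pooled, post-treatment and change SDs, only the baseline SD returns both figures, at n=20 and n=16. The sample-size mismatch is a separate matter and is used here only to identify the units. The statement of more than 80% power at 1.37 remains true at n=28, where power is 92%.

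**One change on four scales.** Take a change of 1.79 baseline SDs. This is an illustration, because the documents do not give the units of the cited 1.79.

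| SD ratio k | baseline | pooled | post | change |
|---|---|---|---|---|
| 2 | 1.79 | 1.79/1.581 = 1.13 | 1.79/2 = 0.90 | 1.79/2.069 = 0.87 |
| 1.61 | 1.79 | 1.34 | 1.11 | 1.03 |
| 1.91 | 1.79 | 1.17 | 0.94 | 0.90 |

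The last two rows read the cited 161-191% as post-to-pre ratios, the reading that fits an assumed doubling. If the cited 1.79 were instead in pooled units, the change would be 1.79 × 1.581 = 2.83 baseline SDs and 2.83/2.069 = 1.37 change SDs. What the plan's assumptions fix is the conversion factor of 2.07, not any particular pair of values.

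**Frequency of a reported d of at least 1.37.** In 200,000 simulated bivariate normal trials (n=28, true change 1.79 baseline SDs, k=2, r=0.18) the share is 84% with the baseline SD, 22% pooled, 4% post-treatment and 3% change SD.

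**What depends on the choice.** A test of change compares the mean change with its standard error; the SD used to express d does not enter it. Section VI.C sets no threshold for d and plans no comparison with 1.37 or 1.79. Both figures appear only in Section VI.D, as planning inputs.

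**Covariance structure.** Suppose an equal-variance, equal-correlation model were fitted, with every correlation 0.18, complete data and a week-4 SD of m (assumed; not in the documents). It would estimate the variance of change as the mean of the three pairwise change variances, against a true 4.28. For m=1 that is (1.64 + 4.28 + 4.28)/3 = 3.40, and √(3.40/4.28) = 0.89.

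| m | model variance | SE relative to true | 95% CI coverage | power at 1.37 |
|---|---|---|---|---|
| 1.0 | 3.40 | 0.89 | 92% | 96% |
| 1.5 | 4.05 | 0.97 | 94% | 94% |
| 2.0 | 5.04 | 1.085 | 97% | 90.5% |

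An unstructured model gives 95% coverage throughout and 92% power.

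**The case for a change.** The strongest case for a change is that the choice is open, can roughly halve a headline figure, and would cost one or two sentences to close. The baseline-SD reading is written nowhere. It comes from back-calculation at sample sizes other than the stated 28, so a reader using the plan's own n could not recover it. The simulated shares of 84% against 3% show how far the choice can move a comparison with the cited trials. A transformation under Section VI would also alter the scale of the effect size.

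Much of this stands as description: the SD is unnamed, and a published effect size should state its SD. What does not stand is the consequence. The 84% to 3% spread counts crossings of a line that the plan never applies to its results. The mean HAM-D change in points depends on no choice of SD, and it follows from the visit means that Section VI gives as an example of its summary statistics. Given the pre and post SDs and the correlation as well, any reader can convert one effect size into another. Sections VI.C and VI.D also use the same term for the effect size, so carrying the power section's metric into the analysis is the natural reading, although it is inferred.

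The covariance argument is weaker. It tests a model that the plan does not state, and it needs week-4 SDs and correlations that the documents do not give. It also assumes complete data, whereas the text after Table 1 says that dropouts are expected. Even so, the effect on significance is small.

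**Conclusion.** The omission is real, but it is a reporting detail that an analyst can fill sensibly, and no change to the plan is needed. Under the plan's assumptions (SD doubled, r=0.18), baseline-SD and change-SD effect sizes differ by a factor of 2.07. At SD ratios of 1.61 to 1.91 the factor is 1.74 to 1.99. Each SD considered gives a valid descriptive measure if it is labelled. The significance test, the power statement and the primary endpoints of feasibility and acceptability do not depend on which SD the report uses.

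The unnamed covariance structure is likewise ordinary detail for a 28-person open trial. In the layouts tried, the worst case was a standard error 11% too small with 92% coverage, under a model that the plan does not commit to.

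The conclusion rests on the effect size staying descriptive, as Section VI.C has it, and on the report stating the SD used. The title page calls the document a shortened version, so a fuller plan may already settle both points.
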